4.4 Eligibility Criteria

4.4.1 Inclusion Criteria

The participant must meet all of the inclusion criteria to eligible for this clinical trial:

- 1. Must be deemed to have capacity to provide informed consent;
- 2. Must sign and date the informed consent form;
- 3. Stated willingness to comply with all study procedures;
- 4. Be diagnosed with COPD as per a WCH Respirologist
- 5. Be 40 years or older
- 6. Be a current or ex-smoker
- 7. Have a history of at least 1 COPD exacerbation (requiring prednisone or antibiotic use, or an urgent healthcare visit of any kind) in the previous 12 months

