5.1 Description

MLHC is delivered virtually through one-on-one meetings with the CRE offered over multiple sessions. The full program consists of 6 sessions across 12 weeks, covering all topics (geared towards new COPD diagnosis). The topics covered in the program include: general COPD knowledge, smoking cessation, COPD medications (inhalers, oxygen), physical activity, mental health and wellness, vaccinations, symptom selfmanagement skills (breathing, energy management, symptom monitoring), nutrition, travel, and long-term planning (including end-of-life care). As participants complete their virtual MLHC program with CREs, they will also have access to the Epic Care Companion app developed as a companion app to MLHC. This app will display a section for each MLHC program session completed, along with session-specific educational and self-management tasks for the patient to complete after the session. These will mostly consist of links to session-specific educational content, but there will also be medication reminder notifications, and reminders to discuss specific topics with their respiratory healthcare providers. This app may also contain individualized tasks created between the CRE and MLHC participant during their sessions. A final report of all completed tasks will be generated on program completion and available in the participant's Epic electronic health record, which can be reviewed by their respiratory healthcare providers.

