7.4.3 Analysis of the Secondary Endpoint(s)

Clinical endpoints:

Assessed prior to study start, at 3 months (end of MLHC program) and at 6 months (follow-up after program completion). Outcomes will be collected by MLHC CREs using a standardized form in Salesforce, as well as a research assistant based on Epic electronic chart review. For continuous variables, difference in the mean (SD) will be calculated at 3 months and 6 months compared to baseline. For dichotomous variables, difference in proportions at 3 and 6 months compared to baseline will be calculated.

MLHC study

- Healthcare system utilization (number of COPD-related outpatient visits, hospital admissions, ED visits, ICU admissions (at baseline will be over the previous 12 months)
- COPD severity (CAT and mMRC scores, and number of COPD exacerbations)
- Health related quality of life (CAT score)
- COPD medication use (COPD controller medication use, oxygen therapy, oral corticosteroid use, antibiotic use, rescue inhaler use)
- Smoking status (packs per year, quit attempts)
- Vaccination status (routine guidelines recommended vaccines received)
- COPD knowledge (Adapted COPD-Q score)
- Self-efficacy score (Adapted COPD Self-efficacy scale score)
- Self-management score (Partners in Health Scale score)
- Healthcare provider referrals prior to using the program (pulmonary rehab, smoking cessation counseling referrals

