7.4.4 Safety Analyses

CRE will liaise with clinical team during delivery of MLHC session if any safety concerns arise

At 3- and 6-month follow-up periods, clinical outcomes detailed above will be assessed by study investigators to determine if there are any concerning safety signals (for example, increased exacerbation rates or health service use, COPD severity scores).

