8.5 Safety Management Plan

Participants will be followed bi-weekly by CREs during their participation in the MLHC virtual program. Should any safety concerns arise during this period of the study in relation to COPD severity, exacerbations, or increased healthcare visits, CREs will contact the study team and cases will be discussed on an individual basis. The study team will then liaise with the participant's regular health care team to arrange any necessary follow-up. Following completion of the program, participants will be assessed for clinical outcomes at 3 months and 6 months post-study initiation, at which time safety concerns will also be evaluated, and communicated with the study PI as needed. The study team will then liaise with the participant's regular health care team to arrange any necessary follow-up. As the intervention being delivered represents guideline-based self-management and education support, there is unlikely to be any harm associated with it (this is supported by recent systematic review and meta-analysis data of selfmanagement interventions in COPD). However, though the study is not powered to detect clinical effectiveness, if there are any safety concerns related to study participation at follow-up visits in terms of increased health service use and COPD severity (ED visits, hospitalizations, COPD exacerbations), these will be communicated to the study team, REB and the next appropriate steps will be considered, including but not limited to study termination.

MLHC study

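### The utilization endpoint counts planned and unscheduled COPD outpatient visits together, and sections 7.4.4 and 8.5 describe the safety review of service use in different terms

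*Protocol*

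**What the plan says.** Sections 3.3 and 7.4.3 of the protocol list the utilization outcome as "Healthcare system utilization (number of COPD-related outpatient visits, hospital admissions, ED visits, ICU admissions", with the baseline covering the previous 12 months. The Clinical Trial Summary places it among the effectiveness outcomes, and section 2.2 places it under potential clinical benefit. The four counts are listed one by one. No composite is defined, outpatient visits are not split by type, and no direction of benefit is given for them.

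Section 5.1 says that the app carries "reminders to discuss specific topics with their respiratory healthcare providers". Referrals are another outcome under the same objective: pulmonary rehabilitation and smoking cessation counselling in 7.4.3, with specialist care added in the Summary.

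Service use is described for safety purposes in three places:

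- Section 7.4.4, at 3 and 6 months: "clinical outcomes detailed above will be assessed by study investigators to determine if there are any concerning safety signals", with the examples "increased exacerbation rates or health service use, COPD severity scores".
- Section 8.5, while the program is running: if concerns arise about COPD severity, "exacerbations, or increased healthcare visits, CREs will contact the study team", and cases are discussed individually.
- Section 8.5, at the follow-up visits: "increased health service use and COPD severity (ED visits, hospitalizations, COPD exacerbations", with study termination among the possible next steps.

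Section 3.1 states that there is no control group.

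**The concern.** An outpatient visit can mean two opposite things here. It can be care the program encourages: a topic raised with a provider after a reminder, or a rehabilitation, counselling or specialist appointment that follows a referral. It can also be an unscheduled visit because the disease is worse. The endpoint adds both into one number. A concurrent control group would at least show whether the program changed that number. A single-arm before-after comparison shows neither that nor which kind of visit moved.

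Three things are at stake. First, the outpatient component is hard to interpret for the secondary objective. Second, section 7.2 says the results will inform the sample size of a later controlled trial, so an ambiguous measure could be carried forward. Third, the investigators who review safety do not have one description of which service use they are to look at. Section 8.5 also has the study team arrange follow-up care when a concern arises, and that care may add to the same outpatient count.

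**Working it through.** **Safety wording, side by side**

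| Place | When | Service use described | Outpatient visits included? |
|---|---|---|---|
| 7.4.4 | 3 and 6 months | All the clinical outcomes; increased health service use given as an example | Yes, through 7.4.3 |
| 8.5, program phase | During the 12 weeks | Increased healthcare visits | Not excluded |
| 8.5, follow-up | 3 and 6 months | ED visits, hospitalizations, exacerbations in parentheses | Not named |

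The first and third rows cover the same assessments in different terms. The second and third stand in the same section and differ in breadth.

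**Is there a figure to reproduce?** No. The protocol gives no visit rate, expected change or threshold. The sample size of 50 has no stated inputs, and the point does not depend on it. What follows is an illustration on assumed rates.

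**Effect of one prompted visit per participant.** Let b be baseline outpatient visits per year (assumed 1, 2, 4 or 6), e the extra prompted visits in the window (assumed 1), and w the window in months (3 or 6, both counted from baseline, which is also an assumption).

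- Raw count in the window = b × w/12 + e
- Annualised rate = raw count × 12/w = b + 12e/w
- Relative rise in the annualised rate = 12e/(w × b)

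For b = 2 and w = 6: raw count = 2 × 6/12 + 1 = 2.00; annualised rate = 2 + 12/6 = 4.0; rise = 12/(6 × 2) = 100%.

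| b per year | 3-month count | 3-month annualised | 6-month count | 6-month annualised |
|---|---|---|---|---|
| 1 | 1.25 | 5.0 (+400%) | 1.50 | 3.0 (+200%) |
| 2 | 1.50 | 6.0 (+200%) | 2.00 | 4.0 (+100%) |
| 4 | 2.00 | 8.0 (+100%) | 3.00 | 6.0 (+50%) |
| 6 | 2.50 | 10.0 (+67%) | 4.00 | 8.0 (+33%) |

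On equal time, prompted contact alone could look like a marked increase in service use. If raw counts are instead set against the 12-month baseline, as the text can be read, the visit rate must exceed 12/3 = 4 times baseline at 3 months, or 12/6 = 2 times at 6 months, before any rise shows. The extra visit then appears as a rise only at b = 1. At b = 2 to 6 it appears as no change or a fall. The direction of the displayed result therefore depends on the time scale, and neither scale separates planned from unscheduled visits.

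**Planned against unscheduled contact.** With 50 participants and an assumed 0.25 to 1 prompted visit each over six months, prompted visits number 50 × 0.25 = 12.5 to 50 × 1 = 50. With an assumed 0.25 to 1 unscheduled contact each and an assumed 30% fall, 0.30 × 12.5 = 3.75 to 0.30 × 50 = 15 contacts are avoided. The net change at the four corners of these ranges is:

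- 12.5 − 3.75 = +8.75
- 12.5 − 15 = −2.5
- 50 − 3.75 = +46.25
- 50 − 15 = +35

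Three of the four are increases although unscheduled contact fell. This shows only that the two kinds of visit can move in opposite directions. The protocol does not say it will calculate such a total, and under section 7.3 the clinical outcomes cover completers with follow-up, who may number fewer than 50.

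**The case against.** The strongest reply is that the protocol does not attach the bad reading to outpatient visits. A reader might infer that more outpatient visits would be scored as failure, treated as harm, or lead towards termination. The text does not support that. No direction is stated for outpatient visits, the four counts stay separate, and the only utilization benefit cited, in section 1.5, concerns respiratory hospital admissions. Section 7.4.4 leaves signals to investigator judgement without a threshold. The sentence in 8.5 that mentions termination does not name outpatient visits. All of this stands, and it limits the point to ambiguity.

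The mechanism is also partly inferred. Section 5.1 says the tasks are mainly links to educational material. It describes reminders to discuss topics, not referral prompts, and does not say that reminders cause extra visits. Participants are already followed in the hospital's respirology clinics and could raise topics at existing appointments. Nor does the protocol say that rehabilitation or counselling sessions count as COPD-related outpatient visits. This too stands: prompted visits are plausible, not documented.

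Deterioration is measured in other ways as well: exacerbations, ED visits, admissions, ICU admissions, corticosteroid and antibiotic use, CAT and mMRC. The exacerbation criterion in 4.4.1 already covers events "requiring prednisone or antibiotic use, or an urgent healthcare visit of any kind". If that definition carries over to the endpoint, urgent visits partly overlap the exacerbation count. These measures help with interpretation but do not show what kind of outpatient visit occurred.

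Finally, visit coding might be left to a data collection form or an analysis plan that is not shown. That answers the coding in part. It does not answer the differing safety descriptions, which are in the protocol, and an analysis plan cannot recover a visit type that was never recorded.

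**Conclusion.** The point holds as one of ambiguity and inconsistent wording. As written, the outpatient count cannot separate prompted or planned care from unscheduled care, and a single-arm before-after comparison cannot resolve this. The safety descriptions in 7.4.4 and 8.5 differ and must be reconciled; which set of events is right is not for this review to say.

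The size cannot be derived from the protocol. The 33% to 200% rise at six months (67% to 400% at three) rests on an assumed one prompted visit per participant and 1 to 6 baseline visits a year. The raw-count reading would usually hide that rise. The conclusion does not depend on these rates, only on both kinds of visit being possible within one count.

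The point concerns the secondary objective and the safety wording. It does not affect the primary feasibility endpoints.

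**What to change.** - Add a visit-type field to the Salesforce form and to the Epic chart review: planned (including visits that arise from a referral or reminder) or unscheduled/urgent. The protocol already uses an urgent-visit category in inclusion criterion 7.
- In 3.3 and 7.4.3, report planned outpatient visits separately from unscheduled or urgent ones, and both separately from ED visits, admissions and ICU admissions. State that no direction of benefit is attached to planned visits.
- Give all visit counts as rates over equal time, so that the 12-month baseline and the 3- and 6-month assessments can be compared.
- Reconcile 7.4.4 with both descriptions in 8.5, so that the safety review refers to one stated set of events.

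The cost is one data field and a wording amendment. The small downside is that some visits will need a judgement between planned and urgent, so a short coding rule should be written before data collection starts.

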14.0 CLI		
17.1	- I UINU NO OUNCE	

MLHC study Version date: 28/05/2024

14.2	CONFLICT OF INTEREST	27
15.0 PU	BLICATION POLICY/DATA SHARING	27
15.1	FUTURE SECONDARY USE OF DATA	45
16.0 RF	FERENCES	27

MLHC study Version date: 28/05/2024

STATEMENT OF COMPLIANCE

This clinical trial will be carried out in accordance with the following:

- International Conference on Harmonisation Good Clinical Practice (ICH GCP)
- Tri-Council Policy Statement 2018 (TCPS 2)
- Personal Health Information Protection Act (PHIPA), 2004; Chapter 3 Schedule A (PHIPA) and applicable regulations
- Institutional and REB policies and procedures

/_/_:	
/ //	May 6 th , 2024
Signature of PI	Date

LIST OF ABBREVIATIONS

Include a list of abbreviations used within the research protocol. A sample list is included below:

AE Adverse Event

CRE Certified Respiratory Educator

COPD Chronic Obstructive Pulmonary Disease

CRF Case report form(s)

DSMB Data Safety & Monitoring Board

GCP Good Clinical Practice

ICF Informed consent form

MLHC My Lung Health Coach

PHI Personal Health Information

PHIPA Personal Health Information Protection Act

PI Principal Investigator

QI Qualified Investigator

SAE Serious Adverse Event

SUSAR Suspected unexpected serious adverse reaction

TCPS 2 Tri-Council Policy Statement

CLINICAL TRIAL SUMMARY

Short Title	MLHC clinical study
Phase	Pilot study
Methodology	Single arm pilot study
Clinical trial Duration	12 months
Participating site(s)	Single site – Women's College Hospital
Objectives	To evaluate the feasibility and effectiveness of MLHC, a COPD self-management and education support program delivered virtually with an electronic patient-record integrated companion app
Number of Participants	50
Study Intervention Reference Therapy/Comparator	The intervention will be enrollment in the MLHC program (a COPD self-management and education support program delivered virtually), and access to the Epic Care Companion MLHC companion app. There will not be a control group for this pilot study.
Duration of Intervention	12 weeks intervention duration, 6 months total follow-up

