Feasibility outcomes (system use): Number of patients who started program over total offered Number of patients who completed program over total started Number of providers who referred patients to the program over total App use metrics over duration of study participation Effectiveness outcomes (clinical outcomes): These outcomes will be collected prior to program commencement, at program completion (3 month), and at 6-month follow-up. Outcomes will be collected by MLHC certified respiratory educators (CREs) using a standardized form in Salesforce, as well as a research assistant based on Epic electronic chart review. For continuous variables, difference in the mean (SD) will be calculated at 3 months and 6 months compared to baseline. For dichotomous variables, difference in proportions at 3 and 6 months compared to baseline will be calculated. Healthcare system utilization: number of COPD-Statistical related outpatient visits, hospital admissions, ED Methodology visits, ICU admissions (at baseline will be over the previous 12 months) o COPD severity: CAT and mMRC scores, and number of COPD exacerbations Health-related quality of life: CAT score Medication, smoking, vaccination status: COPD

controller medication use, oxygen therapy, oral corticosteroid use, antibiotic use, rescue inhaler use, packs per year smoking, smoking cessation

Knowledge of COPD: Adapted COPD-Q scoreSelf-efficacy: Adapted COPD Self-Efficacy Scale

Self-management: Partners in Health Scale (PIHS)

Referrals: pulmonary rehab, smoking cessation

attempts, routine vaccinations

counseling, specialist care

(COPD SES) score

score

MLHC study

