3.3 Secondary Endpoints

Clinical endpoints:

MLHC study

- Assessed prior to study start, at 3 months (end of MLHC program) and at 6 months (follow-up after program completion). Outcomes will be collected by MLHC CREs using a standardized form in Salesforce, as well as a research assistant based on Epic electronic chart review. For continuous variables, difference in the mean (SD) will be calculated at 3 months and 6 months compared to baseline. For dichotomous variables, difference in proportions at 3 and 6 months compared to baseline will be calculated.
 - Healthcare system utilization (number of COPD-related outpatient visits, hospital admissions, ED visits, ICU admissions (at baseline will be over the previous 12 months)
 - COPD severity (CAT and mMRC scores, and number of COPD exacerbations)
 - Health related quality of life (CAT score)
 - COPD medication use (COPD controller medication use, oxygen therapy, oral corticosteroid use, antibiotic use, rescue inhaler use)
 - Smoking status (packs per year, quit attempts)
 - Vaccination status (routine guidelines recommended vaccines received)
 - COPD knowledge (Adapted COPD-Q score)
 - Self-efficacy score (Adaptd COPD Self-efficacy scale score)
 - Self-management score (Partners in Health Scale score)
 - Healthcare provider referrals prior to using the program (pulmonary rehab, smoking cessation counseling referrals

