6.0 RESEARCH PROCEDURES

6.1 Research Visits

- Pre-Screening Visit / Screening Visit (virtual or in-person)
 - Informed consent
 - Review of eligibility criteria
 - Orientation to the Epic Care Companion MLHC companion app
 - This visit will be performed by study staff (research assistant, or study investigators)
- Baseline Visit (virtual)
 - Collection of baseline outcome data
 - This visit will be performed by CREs as part of the MLHC program, study staff (research assistant, or study investigators) will confirm data collection and if needed supplement data collection using Epic or by contacting the participant

MLHC study

- Delivery of MLHC program 6 virtual sessions over 12 weeks, delivered by CREs, no outcome collection during this phase of the study
- Follow-up Visit at 3 months post baseline (virtual)
 - o Collection of follow-up outcome data
 - This visit will be performed by CREs as part of the MLHC program, study staff (research assistant, or study investigators) will confirm data collection and if needed supplement data collection using Epic or by contacting the participant
- Follow-Up Visit at 6 months post baseline (virtual)
 - o Collection of follow-up outcome data
 - This visit will be performed by CREs as part of the MLHC program, study staff (research assistant, or study investigators) will confirm data collection and if needed supplement data collection using Epic or by contacting the participant

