6.2 Schedule of Events

Procedures	Screening Day -7 to -1	Baseline Visit 1, Day 1	Study Visit 2, 3 months	Study Visit 3, 6 months
Informed consent	X			
Confirming eligibility	X			
MLHC companion app orientation	X			
Demographic information	X			
Health system utilization		Χ	X	X
COPD severity (CAT and mMRC scores)		X	Х	X
Health-related quality of life (CAT score)		X	X	X
Mediation review		X	X	X
Smoking status review		Χ	X	X
Vaccination status review		Χ	X	X
Adapted COPD-Q score (knowledge of COPD)		Χ	X	X
Adapted COPD Self-Efficacy score		Χ	X	X
Partners in Health Scale score (self-management)		Χ	Χ	X
COPD referrals review (rehab, smoking cessation)		X	X	X
Adverse event review and evaluation		X	Х	X
Complete Case Report Forms (CRFs)	X	X	X	X

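### Health service use is counted over 12 months at baseline but has no stated window at 3 and 6 months, and the before-after differences are not scaled for time

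*Protocol*

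**What the plan says.** Three places in the protocol define the utilization outcome, and each ties the 12-month window to baseline:

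- Section 7.4.3: "hospital admissions, ED visits, ICU admissions (at baseline will be over the previous 12 months".
- Section 3.3: "ICU admissions (at baseline will be over the previous 12 months".
- Clinical Trial Summary, statistical methodology: "visits, ICU admissions (at baseline will be over the previous 12 months".

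The Summary gives the time frame as "12 weeks intervention duration, 6 months total follow-up". Section 6.1 schedules a "Follow-up Visit at 3 months post baseline (virtual") and a matching visit at 6 months. The Section 6.2 row "Health system utilization" is marked at baseline, 3 months and 6 months. Neither section says what period the follow-up counts cover.

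Section 7.4.3 names two comparisons: "For continuous variables, difference in the mean (SD) will be calculated at 3 months and 6 months compared to baseline", and "For dichotomous variables, difference in proportions at 3 and 6 months compared to baseline will be calculated". It does not say which applies to event counts. Section 7.4.4 mentions exacerbation rates as an example of a safety signal, but no section defines a rate, a denominator or person-time. The number of exacerbations is listed under COPD severity with no window at any visit. Section 3.1 states that there is no control group.

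**The concern.** A count over 12 months cannot be compared directly with a count over 3 or 6 months. The baseline window is fixed at 12 months, follow-up cannot exceed 6, and the named differences are raw. The natural reading of the follow-up counts, events since baseline, therefore makes a program with no effect look like a large reduction in health service use.

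Three features of the trial raise the stakes:

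- The before-after contrast is the only one, so no comparator would reveal the artefact.
- Section 2.2 lists utilization first among the clinical outcomes, and Section 7.2 says the results will inform sample size calculations for a later controlled trial. A spurious reduction could carry into that design.
- Sections 7.4.4 and 8.5 look for increased health service use as a safety concern. The protocol does not say that this review uses the raw counts. If it does, a real increase would be masked in the same direction.

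The exacerbation count has the same problem if its baseline value is the 12-month history required by inclusion criterion 7.

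**Working it through.** The protocol gives no expected count, rate or effect for this outcome, so there is no figure of its own to reproduce. The check is direct arithmetic.

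**Inputs.** Baseline window: 12 months (Summary, 3.3, 7.4.3). Follow-up visits: 3 and 6 months after baseline (6.1). Comparison: unscaled difference from baseline (7.4.3). Follow-up window: not stated, so each plausible reading is tried. Let *m* be the true event rate after baseline divided by the rate before it.

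**Difference in means.** Ratio of the expected follow-up count to the expected baseline count:

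- Events since baseline: *m* × 3/12 at 3 months and *m* × 6/12 at 6 months.
- Events since the last visit: *m* × 3/12 at both visits.
- Rolling 12-month look-back: (9 + 3*m*)/12 at 3 months and (6 + 6*m*)/12 at 6 months.

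| Reading | Unchanged rate (*m* = 1): 3 mo, 6 mo | Doubled rate (*m* = 2): 3 mo, 6 mo |
|---|---|---|
| Since baseline | 0.25, 0.50 (falls of 75%, 50%) | 0.50, 1.00 (fall of 50%, no change) |
| Since last visit | 0.25, 0.25 (falls of 75%, 75%) | 0.50, 0.50 (falls of 50%, 50%) |
| Rolling 12 months | 1.00, 1.00 (no change) | 1.25, 1.50 |

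These ratios do not depend on the event rate. At 1 event per year, for example, the mean goes from 1.00 to 0.25 and 0.50. Counting since baseline, the true rate would have to rise 12/3 = 4-fold at 3 months, or 12/6 = 2-fold at 6 months, before the raw mean even equalled baseline.

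Under the rolling look-back, 9 of the 12 months at the 3-month visit and 6 of the 12 at the 6-month visit lie before the program, which is why a real change is diluted.

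**Difference in proportions.** If the counts were reduced to any event versus none, the proportion under a Poisson model is 1 − exp(−*r* × *t*), with *t* = 1, 0.25 and 0.5 years. The protocol gives no utilization rate, so *r* is an assumption. For an unchanged rate, counting since baseline:

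| Assumed *r* per year | Baseline, 12 mo | 0–3 mo | 0–6 mo |
|---|---|---|---|
| 0.2 | 18% | 5% | 10% |
| 0.5 | 39% | 12% | 22% |
| 1 | 63% | 22% | 39% |
| 2 | 86% | 39% | 63% |

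Allowing for variation between patients (gamma-Poisson, mean 1, shape 1), the formula becomes 1 − 1/(1 + *t*), giving 50%, 20% and 33%. The false fall remains. The entry criteria are not modelled.

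**After scaling.** Multiplying each count by 12/window gives an expected difference of zero at both visits when the rate is unchanged, whatever the rate.

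**The case against.** The strongest reply is that the 75% and 50% figures need a follow-up window the protocol never states. Look-back periods and annualization are often left to an SAP or a data collection form, and Section 10.1 refers to a data management plan and a collection form that are not shown. This stands as a limit on the figures: they are conditional on counting since baseline. It does not remove the problem. The protocol is not merely silent, because it fixes a 12-month window for baseline alone and pairs it with unscaled differences. The other readings tried give either a false fall or a diluted change.

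Other points carry some weight:

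- Utilization is defined as a number of events, so the rule for proportions may not apply to it. The proportions above only show that dichotomizing would not cure the mismatch.
- The exacerbation point is conditional, since no window is stated for that count.
- The safety point is weak support. Section 8.5 has the educators in contact every two weeks with cases discussed individually, and Section 8.2 requires adverse event questioning at each contact. Neither depends on these counts, nor do serious adverse event reporting and the CAT and mMRC scores.
- Regression to the mean is a separate issue that would remain with matched windows.
- Section 7.3 limits the clinical analysis to completers with follow-up, so exposure is nearly uniform and any common time base would serve as well as person-years.
- These are unpowered secondary outcomes in a feasibility pilot. That limits the weight of the point, but the repair is correspondingly small.

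**Conclusion.** The concern holds. As written, the plan sets a 12-month baseline count against follow-up counts of unstated duration, using differences that take no account of time. If follow-up events are counted since baseline, an unchanged rate appears as a 75% fall at 3 months and a 50% fall at 6 months; this needs only a constant rate and holds at any level of use. If each visit looks back 12 months, there is no false fall, but only a quarter of a real change in rate shows at 3 months and half at 6 months. That the windows are not aligned is certain from the text; the size of the distortion depends on which window is used. It should be fixed because the before-after comparison of health service use cannot otherwise be interpreted. The primary feasibility endpoints are not affected.

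**What to change.** In the Clinical Trial Summary and Sections 3.3 and 7.4.3, state the look-back at each visit for both utilization and exacerbations: 12 months before baseline, baseline to 3 months, and baseline to 6 months. Put the same periods on the data collection forms, since a period not fixed at collection may not be recoverable later.

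Report events per person-year, or on another common time base, with a rate difference or rate ratio and its 95% confidence interval. Use those rates wherever Sections 7.4.4 and 8.5 refer to increased use.

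Add one sentence of caution. Inclusion criterion 7 requires an exacerbation in the prior 12 months, and exclusion criterion 1 bars one in the last 4 weeks. Some fall is therefore expected from regression to the mean even after scaling, and the before-after change should be read accordingly.

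The cost is wording in five places, a stated period on the forms, and a little more analysis. Visits, sample size and participant procedures do not change. The downside for the investigators is that reported reductions will be smaller.
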